#### 1.3 Schedule of Activities

Table 1 through Table 8 list all of the assessments and indicate with an "X" the evaluations performed by visit.

- Table 1: Visit Evaluation Schedule Dose Escalation Part
- Table 2: PK, ADA and ECG Sampling Dose Escalation Part
- Table 3: Vital Signs Dose Escalation Part
- Table 4: Biomarker Table Dose Escalation Part
- Table 5: Visit Evaluation Schedule Expansion Part
- Table 6: PK, ADA and ECG Sampling Expansion Part
- Table 7: Vital Signs Expansion Part
- Table 8: Biomarker Table Expansion Part

In addition to the fixed visits, it may be necessary to perform some of the assessments at unscheduled time points if deemed clinically necessary by the investigator. All data obtained from these assessments must be supported in the subject's source documentation.

Document Number: TMF-34513

**Table 1** Visit Evaluation Schedule – Dose Escalation Part

Treatment Cycle (C)	Notes	Section Reference	Screening					Cycl	e 1							Cycle	2		
Day (d)/Week (wk)			≤ 28d prior to C1 (1d)	1d	2d	4d	8d	9d	11d	15d	16d	18d	1d	2d	4d	8d	9d	11d	15d
Visit window							+1d			+1d			+2d			+2d			+2d
Informed Consent		13.2.3	X																
Eligibility Criteria		5.1, 5.2	X																
Demographics		9.1.1	X																
Medical History		9.1.2 to 9.1.5	X																
Body weight		9.3.2	X																
Physical Examination	After Screening, perform exam only as indicated by subject's symptoms, AEs, or findings as determined by investigator.	9.3.1	X	X			X			X			X			X			X
Vital Signs	See Table 3 for GEN1044 dosing days. At Unscheduled visit, perform only as indicated by subject's symptoms, AEs, or findings as determined by investigator.	9.3.3	X	X			X			X			X			X			X
ICE Score Assessment	See Table 18.	10.4.2	X	X			X			X			X						
ECG	See Table 2	9.3.4	X																
Radiological Exam/Tumor Imaging	Imaging is calendar based. On-treatment imaging every 6 wks (±7d) for the first 36 wks (calculated from C1D1), then every 12 wks (±7d) until PD, start of new anticancer therapy, consent withdrawn, or death, whichever occurs first.	9.2.1	Xª																
Whole-body Bone Scan	Subjects with prostate cancer. Ontreatment scans every 6 wks (±7d) (or longer per local standards) for the first 24 wks(calculated from C1D1), then every 12 wks (±7d) until PD, start of new anticancer therapy, consent withdrawn, or death, whichever occurs first.	9.2.1	X																

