ECOG-PS	Do not perform C1D1 ECOG-PS if within 5 days of Screening ECOG-PS. C1D1 ECOG-PS must be within 0-1 or subject cannot receive GEN1044. At Unscheduled visit, only if relevant.	9.3.5	X	X									X						

Document Number: TMF-34513

Treatment Cycle (C)	Notes	Section Reference	Screening					Cyclo	e 1							Cycle	2		
Day (d)/Week (wk)			≤ 28d prior to C1 (1d)	1d	2d	4d	8d	9d	11d	15d	16d	18d	1d	2d	4d	8d	9d	11d	15d
Visit window							+1d			+1d			+2d			+2d			+2d
Adverse Events	See footnote "b." Report all AEs from first GEN1044 dose (C1D1) until 30 days after the last GEN1044 dose (ie, Safety Follow-up visit). After SFU only report suspected GEN1044-related SAEs.	10.1, 10.2	Xb	X	X	X	X	X	X	X	X	X	X	X	X	X		X	X
Concomitant Medication		6.5, 9.1.4	X	X	X	X	X	X	X	X	X	X	X	X	X	X		X	X
Premedication with Corticosteroids, Antihistamines and Antipyretics	Premedication is mandatory 30 to 120 minutes prior to first 3 administrations of GEN1044.	6.2, 6.5		X			X			X									
GEN1044 Administration g		6.3, 6.6		X			X			X			X			X			X
LABORATORY AS	SSESSMENTS																		
Hematology	At Unscheduled visit, only if relevant.	9.4	Xc	X	X	X	X	X	X	X	X	X	X			X			X
Biochemistry	At Unscheduled visit, only if relevant.	9.4	Xc	X	X	X	X	X	X	X	X	X	X		X	X		X	X
Coagulation factors	At Unscheduled visit, only if relevant.	9.4	Xc										X						
Urinalysis	At Unscheduled visit, only if relevant.	9.4	X c																
Pregnancy test	At Unscheduled visit, only if relevant.	9.4	X c																
Hepatitis B	At Unscheduled visit, only if relevant.	9.4	Xc																
T3, T4	At Unscheduled visit, only if relevant.	9.4	Xc																
PK/ADA sampling	See Table 2	9.5, 9.6																	
Tumor biopsy, biomarkers	See Table 8	9.7																	
PSA	Subjects with prostate cancer; central lab	9.2.2	Xc	X									X						
Serum testosterone	Subjects with prostate cancer; central lab	9.4.1	Xc																

Document Number: TMF-34513

 Table 1
 Visit Evaluation Schedule - Dose Escalation Part (Continued)

Treatment Cycle (C)	Notes	Section Reference	Cycle	3 to C	ycle 4	Cyc	le 5 to	PDf	Treatment Discontin- uation visit	Safety Follow-up visit	Survival Follow-up	Unscheduled
Day (d)/Week (wk)			1d	8d	15d	1d	8d	15d	-	30d after last dose	Every 12 wk after last dose	
Visit window			+3d	+1d	+3d	+3d	+3d	+3d		+14d	+7d	
Body weight		9.3.2							X			

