#### 7 DOSE MODIFICATIONS AND SAFETY MANAGEMENT GUIDELINES

# 7.1 **Dose-Limiting Toxicity**

The DLT evaluation period is defined as the period from the start of the first GEN1044 administration on C1D1 of the Dose Escalation part of the trial until 7 days after the first full dose. As described in Section 4.1, if a subject receives the priming dose on C1D1, one intermediate dose on C1D8, and the full dose starting on C1D15, the DLT period will be the first 21 days of Cycle 1 (Cycle 1 days 1 through 21). If a subject receives the priming dose on C1D1, the first intermediate dose on C1D8, the second intermediate dose on C1D15, and the first full dose on C2D1, the DLT period will be Cycle 1 up to and including C2D7 (ie, a total of 28 days). The DLT evaluation period may be adjusted for potential GEN1044 treatment delay as described in Section 11.1.7.

National Cancer Institute (NCI) Common Terminology Criteria for Adverse Events (CTCAE) v5.0 (NCI-CTCAE, 2017) will be used to assess toxicities/AEs, except for CRS and immune effector cell-associated neurotoxicity syndrome (ICANS) (see Section 10.4.1 and Section 10.4.2, respectively).

A DEC is set up for the study. The DEC will review data from each DL cohort and make a decision regarding dose escalation. That decision of the DEC has to be confirmed by the sponsor SC. The DMC will review data on a quarterly basis.

Events to be collected and assessed by the DMC for DLTs include: SAEs; AESIs where applicable; and clinically significant abnormal laboratory values (that are not already covered by a separate AE term).

The occurrence of any of the toxicities outlined in this section will be considered a DLT if assessed by the investigator to be at least possibly related to GEN1044. AEs clearly not related to the trial treatment (GEN1044) such as disease progression, environmental factors, unrelated trauma, etc, should not be considered a toxicity event.

The following will qualify for a DLT:

- ≥ Grade 3 CRS, graded according to American Society for Transplantation and Cellular Therapy (ASTCT) criteria (Lee et al., 2019) (see Section 10.4.1, Table 16).
- \geq Grade 3 ICANS, graded according to the criteria specified in Table 17, Section 10.4.2.
- Any Grade 3 or 4 non-hematologic toxicity except for:
  - Grade ≥ 3 nausea/vomiting or diarrhea <72 hours with adequate anti-emetic and other supportive care
  - Grade  $\geq$  3 fatigue  $\leq$ 1 week

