  - Grade ≥ 3 electrolyte abnormality that lasts <72 hours, unless the patient has clinical symptoms, in which case all grade ≥3 electrolyte abnormality regardless of duration should count as a DLT
  - Grade ≥ 3 amylase or lipase elevation NOT associated with symptoms or clinical manifestations of pancreatitis does not need to be counted as a DLT
  - o Laboratory abnormalities are excluded except for below:
    - Clinically significant medical intervention is required to treat the subject, OR
    - The abnormality leads to hospitalization, OR
    - The abnormality persists for >1 week, OR
    - The abnormality results in a drug-induced liver injury (DILI)
- Any Grade 3 or 4 hematologic toxicity, except for:

Version: 4.0

- Grade  $\geq$  3 lymphocytopenia lasting  $\leq$ 72 hours
- Grade 3 thrombocytopenia not associated with impaired hemostasis, clinically significant bleeding or required platelet transfusion therapy
- Grade  $\geq$  3 ANC lasting <7 days and without fever
- Grade 3 or grade 4 febrile neutropenia:
  - o Grade 3 is defined as absolute neutrophil count (ANC) <1000/mm³ with a single temperature of >38.3°C (101°F) or a sustained temperature of ≥38°C (100.4°F) for more than 1 hour.
  - o Grade 4 is defined as ANC <500/mm³ with a single temperature of >38.3°C (101°F) or a sustained temperature of ≥38°C (100.4°F) for more than 1 hour, with life-threatening consequences and urgent intervention indicated.
- Liver toxicity as defined by Hy's Law (FDA-Guidance, 2009) below:
  - o Aminotransferase (ALT and/or AST) >3×ULN.
  - o Total bilirubin >2×ULN, without initial findings of cholestasis (elevated serum alkaline phosphatase).
  - No other reason can be found to explain the combination of increased ALT/AST and total bilirubin.
- Any treatment-related toxicity that causes the subject to discontinue treatment during Cycle 1.
- Any grade 5 toxicity.

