#### 11.1.7 Dose-Determining Analysis Set – Dose Escalation Part

The dose-determining set (DDS), which is used to define the number of DLT evaluable subjects on a DL cohort, will include all FAS subjects in the escalation part who meet the exposure criterion (defined below) and have sufficient safety evaluations, or experience a DLT prior to the 2nd full dose administration. The DLT period will extend until 7 days after the first full dose (see Section 4.2).

A subject meets the exposure criterion if all doses, up to and including the 1st full dose, are administered in a timely fashion: In general, the individual doses should not be delayed more than 7 days. However, longer dose delays might be acceptable if the DEC considers the assessments still to be appropriate. The first full dose should be administered at latest by 30 calendar days after C1D1 (if one intermediate dose is administered), or by 38 calendar days after C1D1 (if two intermediate doses are administered), counting the day of first exposure as C1D1.

If there is a longer dose delay the subject is considered as non-DLT evaluable (as long as the reason for the dose delay, or the dose delay itself, is not classified as a DLT). DLTs occurring beyond the DLT period will be presented, but not contribute to the DLT rates for the DL cohort per mBOIN.

Subjects who do not experience a DLT will be considered to have sufficient safety evaluations if they have been observed for  $\ge 21$  days (or  $\ge 28$  days if 2 intermediate doses are applied) following the priming dose, and are considered by both the sponsor and investigators to have enough safety data to conclude that a DLT did not occur.

For a period-specific dose level (doses up to and including 1st full dose), a subject is considered as DLT evaluable if the dose was timely administered (ie, not delayed for more than 7 days) and had sufficient safety evaluations up to the subsequent dose administration to conclude if a DLT did occur or not. The relative DLT periods for priming and intermediate doses extend the planned timing of the subsequent dosing (ie, extends until 7 days after the dose administration). For the 1st full dose, it extends up to 7 days past drug administration. Appendix 9 provides a comparison of the DDS considerations and a template for the reporting of DLT rates.

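### With two intermediate doses, Table 1 schedules no blood count between the C2D1 first full dose and the end of the DLT period on C2D7, and the protocol is unclear whether a C2D8 finding counts

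*Protocol*

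**What the plan says.** Protocol Section 7.1 defines the DLT period by where the first full dose falls. With one intermediate dose it falls on C1D15 and "the DLT period will be the first 21 days of Cycle 1 (Cycle 1 days 1 through 21". With two it falls on C2D1 and "the DLT period will be Cycle 1 up to and including C2D7 (ie, a total of 28 days".

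Section 7.1 counts as a DLT "Any Grade 3 or 4 hematologic toxicity, except for" a short list. That list covers brief lymphocytopenia, grade 3 thrombocytopenia without bleeding, impaired hemostasis or transfusion, and short afebrile neutropenia. Grade 4 thrombocytopenia and grade 3 or 4 anemia are not on it.

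Section 11.1.7 says of later events that "DLTs occurring beyond the DLT period will be presented, but not contribute to the DLT rates for the DL cohort per mBOIN".

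Table 1 (Dose Escalation) has a hematology row that marks all nine Cycle 1 visits but only Days 1, 8 and 15 of Cycle 2. Counts outside the schedule are left to relevance, as the start of the row shows: "Hematology At Unscheduled visit, only if relevant. 9.4 Xc X". Section 9.4 requires hematology to be available and reviewed before each administration.

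**The concern.** Amendment 3 introduced schedules in which the highest dose of the sequence is first given on C2D1. It built up the visits that follow: PK samples on C2D2 and C2D4, and adverse event and medication review on C2D2. Hematology was not carried across, although it is drawn at the matching visits, C1D16 and C1D18, in the one-intermediate schedule.

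A low platelet count or hemoglobin need not cause symptoms, so adverse event review alone may not find it. The DLT is the primary endpoint of the escalation part, and the cohort DLT rate enters the mBOIN rule in Table 11. If one class of DLT is not looked for after the highest dose, that rate may be too low in just these cohorts. The two schedules are also not observed alike. The same weakness affects the fourth-dose row of Table 29.

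**Working it through.** **1. The plan's own window.** With two intermediate doses: 21 days of Cycle 1 + 7 days (C2D1 to C2D7) = 28 days, as stated. C2D1 is trial day 22 and C2D7 is day 28. With one intermediate dose, C1D15 to C1D21 gives a period ending on day 21, also as stated.

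**2. Scheduled visits.** The column order in Table 1 is "≤ 28d prior to C1 (1d) 1d 2d 4d 8d 9d 11d 15d 16d 18d 1d 2d 4d 8d 9d 11d 15d". That is screening, nine Cycle 1 days, then seven Cycle 2 days: 17 columns, which the row entries fill. The table below counts entries strictly after the first full-dose day and on or before the last day of the window.

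| Assessment | One intermediate dose (after C1D15, to C1D21) | Two intermediate doses (after C2D1, to C2D7) |
|---|---|---|
| Hematology | 2 (C1D16, C1D18) | 0 |
| Biochemistry | 2 (C1D16, C1D18) | 1 (C2D4) |
| Adverse event review | 2 (C1D16, C1D18) | 2 (C2D2, C2D4) |
| ICE | 0 | 0 |

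The C2D1 count precedes the first full dose under Section 9.4. The next count is C2D8, nominally trial day 29 and up to day 31 with the +2-day visit window. It is drawn before the second full dose.

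**3. Does a C2D8 finding count?** The wordings differ:
- Section 7.1, explicit day: the period ends on C2D7 (day 28), so C2D8 is outside.
- Section 7.1, general definition, and Section 11.1.7: "The DLT period will extend until 7 days after the first full dose". Seven days after day 22 is day 22 + 7 = 29, which is C2D8. Table 28 likewise allows up to seven days past the dose.
- Section 11.1.7 also admits to the dose-determining set a subject whose DLT precedes the second full dose. A pre-dose C2D8 finding would meet that.

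**4. Effect on the decision.** For three evaluable subjects, Table 11 says escalate at 0 DLTs, remain at 1, de-escalate at 2. One missed DLT turns 1/3 into 0/3 (remain becomes escalate) or 2/3 into 1/3 (de-escalate becomes remain).

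**5. Illustration only.** The documents do not say what share of DLTs would be laboratory-only. Let f be an assumed share of DLTs unseen in the window, with a true DLT rate equal to the 30% target. Then P(0 of 3 counted) = [1 − 0.30(1 − f)]³:
- f = 0: 0.70³ = 34%
- f = 10%: 0.73³ = 39%
- f = 25%: 0.775³ = 47%
- f = 50%: 0.85³ = 61%

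These figures show direction and sensitivity. They are not estimates for this drug.

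**The case against.** **A C2D8 finding may count.** A reader might infer that anything first seen on C2D8 is lost to the mBOIN rate under Section 11.1.7. The documents do not support that flatly. Only the C2D7 wording excludes it, two other wordings let it in, and Section 11.1.7 speaks of DLTs occurring late, not of those detected late. This part of the objection stands. What remains is that the rule is ambiguous, and that a single C2D8 count can neither date the onset nor detect an event that has already resolved.

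**There are other safeguards.** A DLT-free subject is evaluable only if sponsor and investigators judge the safety data sufficient, and unscheduled counts are allowed. The DEC and Safety Committee review all available data, and Section 4.1 brings late DLT-type events into the RP2D decision. These soften the consequence. None of them schedules a count, so a subject treated exactly to plan can still be scored DLT-free without one after the first full dose.

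**The set of affected events is narrow.** Several hematologic events are exempt in Section 7.1. Lymphocytopenia must last more than 72 hours, which samples on C2D2 and C2D4, nominally 48 hours apart, could not show by themselves. That stands, so the point rests on events such as grade 4 thrombocytopenia and grade 3 or 4 anemia.

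**ICE.** A reader might infer a similar asymmetry from the row that begins "ICE Score Assessment See Table 18. 10.4.2 X". There is none: neither schedule has an ICE assessment after the first full-dose day inside the window. Table 1 also does not say whether the C2D1 assessment precedes or follows the infusion. Section 10.4.2 separately asks for ICANS monitoring.

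**Expansion.** The blank cells recur in Table 5, but the DLT period and mBOIN rule belong to Dose Escalation, so the argument does not extend there.

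**Conclusion.** The point holds for hematology. Under protocol version 4.0, a cohort with two intermediate doses has 0 scheduled counts between the pre-dose C2D1 and pre-dose C2D8 samples, against 2 after the first full dose in the one-intermediate schedule. The cohort DLT rate may therefore be understated, and in a three-subject cohort one missed event is enough to change the Table 11 recommendation. Days are nominal. The reading assumes that sites follow Table 1 and order no extra counts.

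The size of the bias cannot be derived from the documents, because it needs the share of DLTs visible only in the laboratory.

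Nor do the documents support inferring that the DLT rates of the trial as conducted are materially biased. SAP Section 1.2 reports at most one intermediate dose and a stop to enrollment, and SAP Section 5.5 uses a 21-day DLT period. SAP Table 1 does list a 1/5/30/37.5 mg sequence, but with its last two doses in parentheses. The defect lies in the plan, and its realized impact is probably small.

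**What to change.** 1. In protocol Table 1, mark hematology on C2D2 and C2D4 for cohorts whose first full dose is on C2D1, to match C1D16 and C1D18.
2. Reconcile the end of the DLT period across Section 7.1, Section 11.1.7 and Table 28, so that it is clear whether a pre-dose C2D8 finding enters the cohort DLT rate.
3. Secondary, for both schedules: consider ICE at the existing visits after the first full dose (C1D16 and C1D18, or C2D2 and C2D4), and state its timing relative to the infusion on dosing days.

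The cost is a table edit and a wording change. No new visit is needed, because Table 2 already takes PK blood on C2D2 and C2D4. The burden is two extra local blood counts to draw and review per affected subject, plus a short bedside assessment if ICE is added.

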### **4.2 Dose Escalation Part**

The rationale for the starting dose selection is provided in Section 4.6.	

Version: 4.0

The rationale behind implementation of intermediate dose(s) is to mitigate potential AEs (including CRS).

The DLT period will extend from the first dose on C1D1 until 7 days after the first full dose:

The planned doses are:

- a priming dose of 0.3 mg or higher,
- a full dose,
- one, or potentially two, intermediate doses in-between the prime and full dose (if two intermediate doses are used the 1st will be lower than the 2nd). The DLT period will vary, depending on whether one or two intermediate doses are given (see above).

Higher dose levels might be explored depending on accrued data during the escalation part. All doses are fixed doses (not weight adjusted).

The FIH single-subject cohort is planned with a priming dose of 0.3 mg on C1D1, followed by a full dose of 3.0 mg on C1D8 and C1D15.

In the escalation part, the cohort sizes will start with single-subject cohorts. The trigger point to expand a 1-subject cohort into a 3-subject cohort is the observation of any of the following events:

- A grade  $\geq 2$  AE is observed within the DLT period.
- A DLT (see Section 7.1) is observed at any time within the DLT period.

That is, when any of these events occur in a 1-subject cohort, it is expanded by 2 additional subjects. When those subjects have completed their DLT period, the escalation model in Section 4.2.1 is initiated. If the single-subject cohorts reach the maximum dose level (beyond which no escalation is possible), it will be mandatory to expand that cohort size to 3 subjects.

In addition, in the single subject-cohort phase, the next cohort can start only once the DLT period for the previous dose level has been assessed and the next dose level is proposed by the DEC and endorsed by the SC. The DEC will recommend the dose level for the next cohort of subjects to the SC and this will need to be endorsed by the SC prior to using the recommended or higher dose in the next cohort dose level implementation. To supplement routine safety monitoring by the sponsor SC as outlined in this protocol, a DMC will monitor safety data for the trial on a quarterly basis or more frequently as determined by the sponsor. Additional details regarding the DEC, sponsor SC, and the DMC can be found in Section 10.9 and in Section 10.10.

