If any single-subject DL cohort is expanded to a total of 3 subjects (based on the trigger point above being reached), all subsequent DL cohorts will initially have 3 subjects per cohort.

Version: 4.0

The next DL cohort, possibly including a higher full-dose level, can start only once the DLT period for the previous DL cohort has been assessed and the next full-dose level is proposed by the DEC and endorsed by the SC. Parallel cohorts may be initiated at any time, provided the full-dose level of the parallel cohort has already been safety-cleared by the SC and does not equal or surpass the full-dose level in the DL cohort under investigation. The DEC will recommend the full-dose level for the next cohort of subjects, including whether 1 or 2 intermediate doses should be given, to the SC and this will need to be endorsed by the SC prior to using the recommended or higher full-dose in the next cohort dose level implementation. The descriptive DLT tables provided to the DEC (see Appendix 9) will provide an overview of the DLT rates considering the whole DL cohort (as intended in the original protocol), and considering the individual period-specific dose level.

For any DL cohort that enrolls more than 1 subject, there will be a minimum of 24 hours between an individual subject's treatment infusion stop and a subsequent subject's treatment start in the same cohort, to account for any acute safety signals in each new dose level. The 24-hour treatment window between same-cohort subjects will not apply to backfilling cohorts enrolling subjects to be exposed to previously safety-cleared full dose levels.

An overnight stay (24 hours in-hospital observation) will be required for all subjects after administration of GEN1044 on Day 1 and Day 8 during Cycle 1 only and may be required for additional subjects and/or dose levels if recommended by the sponsor SC. If a second intermediate dose is implemented at C1D15, the sponsor may decide to require additional 24-hour hospitalization following this dose administration.

During treatment in the Dose Escalation part, safety assessments will be performed as indicated on Table 1. For the assessments of each cohort, the dose-limiting toxicities (DLTs) will be collected for the first treatment cycle, ie, a DLT evaluation period of 21 days from the priming dose (or 28 days if two intermediate doses are applied).

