### Cohort Size:

In the standard titration part, it is allowed to estimate the DLT rate for the DL cohort if 1 subject is non-DLT evaluable and the remaining 2 subjects are DLT-evaluable, provided that neither of the 2 subjects experienced any grade ≥2 AE within the first 7 days of Cycle 1, or any DLT during the 21-day DLT period. (If a dose level has in total 2 subjects being DLT-evaluable and no DLTs are observed, the BOIN rule is to escalate.)

Also, over-recruitment by 1 subject is allowed, so that each 3-subject cohort may consist of 2 to 4 subjects who are evaluable for DLT.

It is noted that for 5 DLT evaluable subjects, the possibility to "remain" cannot be concluded. (The estimate DLT rate is 0%, 20%, 40%, 60%, 80% or 100%. No estimate within the limit of "remain": [24%, 36%].) In this case, the number of DLT evaluable subjects is brought up to 6 by an additional subject to regain this option.

In case a cohort had less than 3 DLT evaluable subjects, the next DL cohort (on the same dosing sequence) may be enlarged to bring the number of subjects on the dose level up to a multiple of 3.

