## 4.2.2 Other Dose Escalation/De-Escalation Procedures

The following provides a description of the procedures not directly associated with the BOIN as such, but that will impact subject accrual and provisions for dose escalation/de-escalation decisions.

- 1. After completion of the first full dosing of each DL cohort, based on the safety data and the BOIN, the sponsor SC will decide on the dose-level for the next cohort of subjects. Escalation to the next dose-level will not occur until all subjects needed for a specific DL cohort have passed the Cycle 1/DLT evaluation period.
- 2. The Dose Escalation part will be assessed in dose-level cohorts (DL cohorts); initially this will be in done in single-subject cohorts until the trigger point (see Section 4.2) is passed.
  - A single-subject DL cohort may be optionally expanded with up to 2 additional subjects for the purpose of obtaining additional safety, PK, pharmacodynamic, and biomarker data (ie, for a total of 3 subjects in that cohort).
- 3. A subject will be considered as evaluable for dose determination if they experience a DLT or meet the minimum treatment and safety evaluation requirements for the first cycle (refer to Section 7.1).

After completion of the DLT period for each DL cohort, the DEC and sponsor SC will review the data from the DLT period to propose the actual next dose level. Data to be reviewed will include but not be limited to all relevant safety, clinical, PK, biomarker data, and the next dose as suggested by the BOIN strategies.

The RP2D to be used for the Expansion part will be determined at the end of the Dose Escalation part by the DEC and sponsor SC, based on a review of the totality of data, including but not limited to efficacy, safety (including DLTs, AEs, safety laboratory values, and observations made after the end of the DLT evaluation period), biomarker and PK data, and dosing information.

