# 7.2 GEN1044 Dose Modification Guidance and Safety Stopping Criteria

#### 7.2.1 Dose Escalation Part

- In the event a subject experiences an AE that meets DLT criteria as outlined in Section 7.1, treatment must be permanently discontinued (unless the subject per investigator's discretion has recovered or is expected to recover and expected to benefit from continued treatment). GEN1044 should also be held for the following:
  - If platelet count  $<50\times10^9$ /L, hold dose until platelet count is  $\ge50\times10^9$ /L.
  - If febrile neutropenia  $<0.5\times10^9$ /L, hold dose until neutrophil count is  $\ge0.5\times10^9$ /L.
  - o If hemoglobin is  $\leq 8 \text{ g/dL}$  ( $\leq 5 \text{ mmol/L}$ ), hold dose until hemoglobin  $\geq 8 \text{ g/mL}$  ( $\geq 5 \text{ mmol/L}$ ).
  - **Note**: Transfusion with blood products and/or administration with G-CSF is permitted if needed (see Section 6.5.2.2).
- During the trial, a planned dose of GEN1044 can be postponed for up to 6 weeks for an AE, whether it is considered drug-related or not; a delay of >6 weeks requires permanent discontinuation of treatment. The delay might be extended to 12 weeks after consultation with the sponsor medical monitor.
- First episodes of cytokine blockade-refractory grade 3 CRS or ICANS (see Section 10.4.1) lasting >72 hours require permanent discontinuation from trial treatment.
- First episodes of refractory grade 4 CRS or ICANS require permanent discontinuation from trial treatment.
- Refer to Appendix 7, Table 27, for dose modification guidelines for specific adverse events. For dose escalation, these rules will only apply after the DLT period.

Version: 4.0

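### Section 7.1 counts treatment-related discontinuation as a DLT only during Cycle 1, although the DLT period runs to C2D7 with two intermediate doses; separately, the SAP fixes 21 days (minor, no effect on collected data shown)

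*Protocol*

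**What the plan says.** Protocol Section 7.1 starts the DLT period at the first dose on C1D1 and ends it 7 days after the first full dose. With one intermediate dose that is days 1 to 21. With two, "the DLT period will be Cycle 1 up to and including C2D7 (ie, a total of 28 days"). The period may also be adjusted for dosing delay, as set out in Section 11.1.7. The list of DLT criteria that follows includes "Any treatment-related toxicity that causes the subject to discontinue treatment during Cycle 1". No other criterion in the list carries a cycle limit of its own.

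Other places that bear on the window:

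- Section 4.2 explains the first treatment cycle as "a DLT evaluation period of 21 days from the priming dose (or 28 days if two intermediate doses are applied").
- Section 4.2.2 allows escalation only when the required subjects "have passed the Cycle 1/DLT evaluation period".
- Section 4.2.1.1 (Cohort Size) refers to "any DLT during the 21-day DLT period" and does not mention the 28-day case.
- Section 11.1.7 generally accepts delays of up to 7 days per dose and adds: "The first full dose should be administered at latest by 30 calendar days after C1D1 (if one intermediate dose is administered").
- SAP Section 5.5 sets the DLT period at C1D1 to C1D21 and cites protocol Section 7.1 for it. SAP Section 4 uses the same 21 days in the dose-determining set. The SAP lists protocol v3.0 and v4.0 among its sources.
- SAP Section 1.2 reports that enrollment was stopped and that no more than one intermediate dose was tested.

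**The concern.** Section 7.1 treats Cycle 1 and C2D1 to C2D7 as separate stretches of time, so its own wording does not let Cycle 1 stand for the full 28 days. In a two-intermediate sequence the discontinuation criterion therefore lapses just as the first full dose is given. The events that could slip through are related toxicities below grade 3, or higher-grade events inside a listed exception, that nevertheless end treatment in that week. The DLT count is the primary escalation endpoint and the input to Table 11, so one-intermediate and two-intermediate sequences would be counted by different rules over the days that matter most.

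The fixed 21 days in the SAP is a separate mismatch with a different mechanism. It also arises in one-intermediate sequences whenever the first full dose is late. What is at stake there is the DLT table in the abbreviated CSR.

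**Working it through.** **1. The plan's own windows.** Take C1D1 as day 1, with 21-day cycles and weekly doses (Section 4.1). The first full dose falls on day 15 with one intermediate dose and on day 22 (C2D1) with two. Counting the dosing day as the first of the 7 days:

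- one intermediate dose: 15 + 7 − 1 = day 21
- two intermediate doses: 22 + 7 − 1 = day 28

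Both match Section 7.1.

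**2. Reach of the discontinuation criterion, read literally (days 1 to 21).**

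| Sequence, on schedule | Week from first full dose | Days covered |
|---|---|---|
| One intermediate dose | days 15–21 | 7 of 7 |
| Two intermediate doses | days 22–28 | 0 of 7 |

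The uncovered part is 28 − 21 = 7 days, or 7/28 = 25% of the two-intermediate window.

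**3. What one uncounted event does in Table 11.** Section 4.2.1 gives φ = 0.30, φ₁ = 0.6φ = 0.18 and φ₂ = 1.4φ = 0.42. The BOIN thresholds are:

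- λ₁ = ln[(1−φ₁)/(1−φ)] / ln[φ(1−φ₁)/(φ₁(1−φ))] = ln(0.82/0.70) / ln(0.246/0.126) = 0.2365
- λ₂ = ln[(1−φ)/(1−φ₂)] / ln[φ₂(1−φ)/(φ(1−φ₂))] = ln(0.70/0.58) / ln(0.294/0.174) = 0.3585

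These agree with the stated 24% and 36%, and every cell of Table 11 for 3 to 9 subjects can be rebuilt from them and the termination rule. Losing one event then gives:

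| Event counted | Event not counted |
|---|---|
| 1/3 = 33%: remain | 0/3: escalate |
| 2/5 = 40%: de-escalate | 1/5 = 20%: escalate |
| 2/6 = 33%: remain | 1/6 = 17%: escalate |

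The documents give no frequency for such events, so no probability is attached.

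**4. The SAP's fixed 21 days.** With one intermediate dose and the first full dose k days late, the days of the 7-day follow-up inside days 1 to 21 number max(0, 7 − k):

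| k | First full dose | Follow-up | Days inside the SAP window |
|---|---|---|---|
| 0 | day 15 | days 15–21 | 7 |
| 1 | day 16 | days 16–22 | 6 |
| 3 | day 18 | days 18–24 | 4 |
| 7 | day 22 | days 22–28 | 0 |

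A 1-day shift lies within the +1-day visit window in protocol Table 1, and Section 11.1.7 allows considerably later first full doses. With two intermediate doses on schedule the SAP window again holds 0 of 7.

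**5. Why the SAP cannot simply adopt the rule of 7 days after the first full dose.** Section 4.2 treats the 3.0 mg dose on C1D8 of the first-in-human cohort (0.3/3/3 mg) as a full dose. SAP Table 1 shows the same pattern for 1/5/5 mg. For these cohorts the rule ends the window on day 8 + 7 − 1 = 14 and drops days 15 to 21, which the SAP now covers. Taking the later date repairs this: max(21, 14) = 21.

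**The case against.** The best defence is that the protocol answers the question itself. Section 4.2 equates the first treatment cycle with 21 or 28 days, Section 4.2.2 joins Cycle 1 and the DLT evaluation period in one phrase, and Section 11.1.7 and Appendix 9 repeat the rule of 7 days after the first full dose. A dose escalation committee reading all of these would probably take Cycle 1 to mean the whole window.

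The gap is also narrow. All other DLT criteria still apply on days 22 to 28. In a single-subject cohort any grade 2 or higher "AE is observed within the DLT period" triggers expansion. A toxicity need not end treatment, because "a planned dose of GEN1044 can be postponed for up to 6 weeks for an AE". Table 11 only recommends; the committees weigh all available data, including later observations when the RP2D is chosen.

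This stands as an account of intent and as a limit on size. It does not change the criterion that investigators apply, and the safeguards rest on judgement rather than on the definition.

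Three stronger readings are tempting, and the documents support none of them:

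- That DLTs were missed in this trial. SAP Section 1.2 says at most one intermediate dose was tested, and for those sequences on schedule Cycle 1 and the DLT period coincide.
- That the week after C2D1 is free of DLT assessment. Only one criterion lapses.
- That the SAP window distorted escalation. This SAP version was written for an abbreviated CSR after enrollment had stopped, so it can change only the tabulation. TEAEs leading to withdrawal from treatment are summarized in any case.

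**Conclusion.** The Section 7.1 criterion is wrong as written, and the error is minor. It is most likely wording left over when Amendment 3 extended the DLT period for a second intermediate dose. Its reach is one criterion over 7 days, in two-intermediate sequences only. The Table 11 shifts above are illustrations, not estimates.

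The SAP mismatch is also real, and it is confined to the DLT table in the abbreviated CSR.

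That no effect on collected data is shown rests on SAP Section 1.2, with two reservations. The 1/5/30/37.5 mg row of SAP Table 1 puts its third and fourth doses in parentheses with an asterisk, and the matching footnote is not in the available text, so it is unconfirmed whether anyone received a second intermediate dose. Nor do the documents say how many first full doses were late, or which subjects were treated under protocol v3.0 and which under v4.0.

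**What to change.** - **Protocol Section 7.1:** in the discontinuation criterion, replace the reference to Cycle 1 with the DLT period.
- **Protocol Section 4.2.1.1, Cohort Size:** delete the 21-day qualifier so that it also refers simply to the DLT period.
- **SAP Sections 4 and 5.5:** define the DLT period as running from C1D1 to the later of (a) day 21, or day 28 with two intermediate doses, and (b) 7 days after the first full dose, adjusted for delay as in protocol Section 11.1.7. State that the prime/full/full cohorts (0.3/3/3 and 1/5/5 mg) keep days 1 to 21.

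The cost is a wording change to one protocol criterion, one protocol label and two SAP definitions, plus a rerun of the DLT table under the corrected window. No visits or subjects are added. With enrollment stopped, the SAP change has the most practical value, since it governs what the abbreviated CSR reports.
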